7 SUBJECT ELIGIBILITY AND WITHDRAWAL CRITERIA

7.1 Number of Subjects

Approximately 60 subjects with diagnosed IPF will be enrolled in the study to ensure evaluable data from at least 44 subjects who complete both treatment periods.

7.2 Inclusion Criteria

Subjects eligible for randomization to receive investigational product must meet all the following criteria:

- 1. Diagnosis of "definite" or "probable" IPF based on ATS/ERS/JRS/ALAT criteria (see *Raghu* et al 2018 in Appendix 6).
- 2. FVC > 40% predicted of normal.
- 3. Diffusing capacity of the lung for carbon monoxide corrected for hemoglobin $[DL_{CO}] > 25\%$ predicted of normal within the past 6 months. Subjects who have not had DLco testing may be enrolled with medical monitor approval.
- 4. Chronic cough > 8 weeks.
- 5. Adequate swallow reflex as assessed by the ability to sip 3 fluid oz (or 89 ml) of water without coughing or choking.
- 6. Daytime cough severity score \geq 4 on Cough Severity Numerical Rating Scale at Screening.
- 7. Males or females age 18 years and older at the time of consent.
- 8. Females of childbearing potential must use an acceptable method of birth control (if sexually active). All females of childbearing potential must have a negative pregnancy test at the screening and baseline visits.

For the purpose of this study, all females are considered to be of childbearing potential unless they are postmenopausal (i.e., at least 1 year since last menses and age > 50 years) or surgically sterile (i.e., tubal ligation, hysterectomy, and/or bilateral oophorectomy).

Sexually active female subjects of childbearing potential are required to use 1 barrier method (e.g., condom, cervical cap, or diaphragm) of contraception in addition to 1 other method (e.g., intrauterine device in place for at least 1-month, stable hormonal contraception for at least 3 months, Essure procedure, or spermicide). For female subjects using a barrier method plus spermicide, that method must be used for at least 14 days prior to Screening.

Female subjects who are abstinent may participate in the study; however, they must be counseled on the requirement to use appropriate contraception should they become sexually active. This counseling should occur at each study visit and must be documented in source records.

- 9. Willing and able to understand and provide written informed consent.
- 10. Willing and able to comply with study requirements and restrictions.
- 11. Agree to the confidential use and storage of all data and use of all anonymized data for publication including scientific publication.

7.3 Exclusion Criteria

Subjects meeting any of the following criteria are not eligible for participation in the study:

- 1. The following conditions are excluded:
 - a) Interstitial lung disease (ILD) known to be caused by domestic and occupational environmental exposures.
 - b) Interstitial lung disease (ILD) known to be caused by connective tissue disease.
 - c) Interstitial lung disease (ILD) known to be caused by drug related toxicity.
- 2. Currently on continuous oxygen therapy for longer than 16 hours at any level or delivered by any modality. Intermittent oxygen use of any duration over any given 24-hr period is allowed.
- 3. Major psychiatric disorder, which in the opinion of the Investigator, could interfere with the assessment of anti-cough efficacy and/or safety events during the study or with the ability of the subject to cooperate with study requirements.
- 4. Serum bilirubin $> 1.5 \times$ upper limit of normal range at screening unless explained by a clinical diagnosis of Gilbert's syndrome.
- 5. Serum hepatic alanine aminotransferase or aspartate aminotransferase enzymes > 100 U/L at Screening.
- 6. Estimated glomerular filtration rate $\leq 44 \text{ mL/min}/1.73 \text{ m}^2$ at Screening.
- 7. Upper or lower respiratory tract infection within 4 weeks of Screening.
- 8. Significant medical condition or other factors that may interfere with the subject's ability to successfully complete the study.
- 9. History of substance abuse that, as determined by the Investigator, may interfere with the conduct of the study.
- 10. Known intolerance or hypersensitivity/drug allergy to nalbuphine or vehicle components.
- 11. Pregnant or lactating female subject.
- 12. Concurrent enrollment in an ongoing clinical trial or anticipated enrollment in a concurrent clinical trial.
- 13. Clinical diagnosis of sleep apnea and/or use of CPAP.
- 14. History of clinically significant head injury in past 1 month.
- 15. Clinical diagnosis of aspiration pneumonitis.
- 16. Clinical history of opiate withdrawal symptoms following use of opiates.
- 17. Documented or clinically suspected hypercapnia ($pCO_2 > 6.0kPa$).

Medication-related Exclusions:

18. Known intolerance (gastrointestinal, central nervous system symptoms) or hypersensitivity/ drug allergy to opioids.

- 19. Exposure to any investigational medication, including placebo, within 4 weeks.
- 20. Potential subjects cannot have received opiates, including opiate-containing anti-cough agents, within 14 days prior to the screening period. Subjects are prohibited from using opioids, including naltrexone, for the duration of the study.
- 21. Potential subjects cannot currently be receiving benzodiazepines or other CNS Depressant Class Drugs that when used concomitantly with opioids are known to have the potential to cause added pharmacologic effects of depressing CNS activity (See Section 9.6.2.2 ("Benzodiazepines and Other CNS Depressant Class Drugs").
- 22. Potential subjects cannot currently be receiving medications that affect serotonergic neurotransmission and that when used concomitantly with opioids can cause serotonin syndrome (See Section 9.6.2.3 ("Serotonergic Class Drugs").
- 23. Alcohol consumption should be limited for the duration of study treatment (due to the potential cause of added pharmacologic effects of CNS depression when used concomitantly with opioids.
- 24. Change of IPF-related drug treatment regimen within 8 weeks of Screening.

Cardiac-related Exclusions:

- 25. Subjects with a history of congestive heart failure of Class 2 or higher as graded using the New York Heart Association classification (*Appendix 8*).
- 26. Subjects with a history of angina pectoris Grade 2 or higher as graded using the Canadian Cardiovascular Society grading scale (*Appendix 7*).
- 27. History of ventricular tachycardia, Torsade de Pointes, or family history of sudden death.
- 28. Myocardial infarction or acute coronary syndrome within the previous 3 months, as reported by the subject.
- 29. Serum potassium below the laboratory lower limit of normal.
- 30. QTcF interval >450 ms (mean of 3 screening ECG QTcF values) if QRS <120 ms (mean of 3 screening ECG QRS values); QTcF interval >480 ms in the presence of Right Bundle Branch Block (RBBB) and/or QRS ≥ 120 ms
- 31. Heart rate < 45 bpm on any screening measurement. Subjects with a resting heart rate of < 45 bpm will have it repeated once after 5 minutes in the supine position, and if it remains < 45 bpm during the repeat, they will be considered a screen failure.
- 32. Use of a medication having a "known risk" of Torsade de Pointes (categorized as "KR" on the Credible Meds[®] website) is not permitted at entry or during the study (See *Appendix 9*).

Medications associated with a potential risk of QT prolongation, but not clearly associated with Torsade de Pointes, are permitted at study entry if the following criteria are met:

- Subject has been given medication at stable doses for a full 4 weeks prior to Screening.
- Medication dose will not be increased after screening, or during the study, and it is anticipated that the subject will receive the medication for the entirety of the study.

7.4 Withdrawal Criteria

Subjects have the right to withdraw from the study at any time for any reason, without prejudice. At any point, the Investigator may discontinue the subject's study participation at his/her discretion and ensure the subject receives appropriate medical care. The Investigator may consult the Medical Monitor to discuss out-of-range test results. The subject may also be withdrawn at the request of the Sponsor. Additionally, although the Sponsor has every intention of completing the study, the Sponsor reserves the right to discontinue the study at any time and for any reason.

Subjects will be withdrawn from the study for any of the following reasons:

- There is deterioration in the subject's signs and symptoms and/or the subject develops a disease or condition that, in the opinion of the Investigator, would compromise the subject's safety by continuing in the study.
- In the Investigator's judgment, it is in the best interest of the subject.
- There is a violation of the protocol inclusion and/or exclusion criteria, as deemed relevant by the Investigator and discussed with the Medical Monitor.
- The subject withdraws consent for study participation.
- Sponsor terminates the study for any reason.
- Develops a QTcF > 500 ms (mean of 3 ECG QTcF values) in subjects who were randomized without ECG findings of RBBB and/or QRS ≥ 120 ms.
- Develops QTcF > 530 ms (mean of 3 ECG QTcF values) in subjects who were randomized with ECG findings of RBBB and/or QRS ≥ 120 ms.
- Increase from QTcF baseline of > 60 ms (mean determination from 3 ECG values)
- Death of the subject.

If a subject withdraws prematurely from the study during a treatment period due to any of the above criteria or any other reason (unless consent is withdrawn), study staff should make every effort (at withdrawal) to have the subject complete as many of the safety assessments including the SOWS, if possible. The reason for subject withdrawal must be documented in the eCRF. Subjects who withdraw from the study will not be replaced.

If a subject is lost to follow-up, attempts to contact the subject must be made and documented in the subject's eCRF.

If the Sponsor decides to terminate the study, the reason(s) for termination will be documented in the source documents and eCRFs.

7.5 Premature Discontinuation of Investigational Product Treatment

Subjects who discontinue investigational product, for reasons other than withdrawal of consent, will be considered to have prematurely discontinued treatment and will be asked to complete the premature discontinuation and 2-week off-treatment safety follow-up evaluations.

8 STUDY ASSESSMENTS AND PROCEDURES

8.1 Efficacy Endpoints

8.1.1 Primary Efficacy Endpoint

The primary efficacy endpoint is the mean change in daytime cough frequency (coughs per hour) from baseline as assessed by objective digital cough monitoring at Day 22 by treatment. Daytime is defined as the time the subject is awake in the 24 hours after the digital cough monitor is applied for use.

8.1.2 Secondary Efficacy Endpoints

The secondary efficacy endpoints are as follows:

- Relative change in daytime cough frequency (coughs per hour) from baseline at Day 22 (dose: 162 mg BID) by treatment.
- Relative change in 24-hour (combined daytime and nighttime) cough frequency (coughs per hour) from baseline at Day 22 (dose: 162 mg BID) by treatment.
- Relative change in nighttime cough frequency (coughs per hour) from baseline at Day 22 (dose: 162 mg BID) by treatment.
- Mean change in the E-RS diary cough subscale (E-RS diary question number 2) from baseline, at Days 9, 16, and 22 by treatment.
- Mean change in the Cough Severity Numerical Rating Scale at Days 8, 15, and 21 by treatment.
- Mean change in the E-RS diary breathlessness subscale (E-RS diary questions 7, 8, 9, 10, and 11) from baseline at Days 9, 16, and 22 by treatment.
- Mean change in the 14-item EXACT v1.1 e-diary tool total score from baseline at Days 9, 16, and 22 by treatment.
- Mean change in the PROMIS Item Bank v1.0 Fatigue Short Form 7a scale from baseline at Day 21 by treatment.
- Mean change in the CGI-C over time measured at Day21 by treatment.

8.2 Efficacy Assessments

Efficacy assessments during each of the 2 treatment periods will include 24-hour digital cough monitoring of cough frequency, a daily e-diary tool, and instruments of patient-reported outcomes.

8.2.1 Digital Cough Monitor

Boulet et al (2015) summarized the CHEST Expert Panel recommendations regarding tools to be used in clinical trials assessing cough. The Panel recommended acoustic cough counting to assess cough frequency should be done through objective means.

Measurement of cough frequency will be done using objective digital cough monitoring. The digital cough monitor consists of a portable sound recording device, which is worn in a pouch or pocket. The small microphone is clipped onto the subject's collar or lapel, as close as possible to the anterior neck. A continuous sound recording is made for up to 36 hours. The digital recording is then processed through accompanying computer software, which automatically registers sound patterns typical for cough. Software output provides the total number of cough events over the entire time period of recording and average hourly cough frequency.

At the baseline visit for each treatment period (the day prior to investigational product initiation), and at subsequent treatment visits, site staff will place the digital cough monitor on the subject prior to their departure from the clinic. The monitor will be worn until the evening of the following day in order to obtain at least a full 24-hour recording period of cough frequency. At the end of each recording session, the monitor will be removed at home by the subject prior to bedtime. On Day 1 of each treatment period, the monitor will be removed prior to taking the first dose of investigational product.

8.2.2 Subject e-Diary

All subjects randomized into the study will be provided with a device with an application for a subject e-diary, along with instructions for its use. The device will be password protected. Subjects will complete daily e-diaries, including compliance with investigational product dosing, and answer study specific questionnaires throughout the duration of the study.

Queries will be handled by the vendor managing the e-diary data through the clinical site. The ediary data will be reviewed by the study staff. The subject will return the e-diary to the site at the follow-up visit of Treatment Period 2 or discontinuation visit.

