6.2 Study Schedule

The schedule of assessments is provided in *Table 1* and *Table 2*.

		Treatment Period 1 ¹						Premature	
	Screening	Baseline			Treatment			Follow-up ²	Discontinuation
Visit:	1	2		3	4	5		6	
	On-Site Visit	On-Site Visit		Phone Visit	Phone Visit	On-Site Visit		On-Site Visit	On-Site Visit
Treatment Day:	-45 to -2	-1	1 ³	8 (+/-1 day)	15 (+/-1day)	21	22 ⁴	36 (+/-2days)	
Informed consent	Х								
Demographics	Х								
Medical history	Х								
Inclusion/exclusion criteria	Х	Х							
Height, weight, and BMI	Х								
Electrocardiogram (triplicate) ⁵	Х							X^{18}	Х
Vital signs ⁶	Х							Х	Х
Spirometry ⁷	Х					Х			
DL _{co} measurement ²⁰	Х								
Swallow test	Х								
Physical examination	Х							X ¹⁸	Х
Urine pregnancy test	Х	X ⁸						Х	Х
Serum pregnancy test	Х								Х
Clinical laboratory tests ⁹	Х					Х			Х
PK blood sampling						Х			
Randomization		Х							
Cough monitor – Dispense/train on use		X ^{10,11}				X ¹¹			
Cough monitor – Removal/return for			v 12				v 12		
downloading of data			Λ^{-}				Λ^{-}		
Cough frequency (via cough monitor)		Х	X ¹²			Х	X ¹²		
Cough Severity Numerical Rating Scale	X ¹³	Х		Х	Х	Х			Х
Fatigue Scale (Short Form 7a)		Х				Х			Х
Clinical Global Impression of Change						Х			
e-diary – Dispense and train on use		Х							
e-diary – Review compliance ¹⁹				Х	Х	Х			
EXACT version 1.1 e-diary tool ¹⁴			<	Recorded	throughout	->			Х
Subjective Opiate Withdrawal Scale						V 15			v 15
e-diary						Λ^{ij}			Λ^{ii}
Contraceptive counseling (if applicable)	Х	Х		X	X	X			
Dispense Subject Medication and Symptom Log	X								

Table 1: Schedule of Events – Screening and Treatment Period 1

			Treatment Period 1 ¹						Premature
	Screening	Baseline			Treatment			Follow-up ²	Discontinuation
Visit:	1	2		3	4	5		6	
	On-Site Visit	On-Site Visit		Phone Visit	Phone Visit	On-Site Visit		On-Site Visit	On-Site Visit
Treatment Day:	-45 to -2	-1	1 ³	8 (+/-1 day)	15 (+/-1day)	21	22 ⁴	36 (+/-2days)	
Subject Medication and Symptom Log – Retrieve/review/re-dispense		Х		X	Х	Х			
Record/assess AEs, conmeds, and therapies (including restricted/prohibited medications) ¹⁶	Х	Х		X	Х	X		Х	Х
Dispense Investigational Product blister card/dosing instructions		Х							
Review Investigational Product compliance				X	X				
Retrieve Investigational Product blister card/review compliance/re-dispense						X		X ¹⁷	X ¹⁷
Retrieval of e-diary, medication and symptom log								Х	Х

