- 14 = E-RS consists of item numbers 1-11 on the 14-item EXACT version 1.1 e-diary tool. E-diary tool will be completed each evening by the subject prior to bedtime. Subject will be reminded to complete this daily at each appropriate study visit.
- 15 = Subjective Opiate Withdrawal Scale will be completed daily via e-diary for 14 days following discontinuation of investigational product regardless of when this occurs (i.e. Day 23 or premature discontinuation). Site will log into the e-diary portal to confirm subject is completing entries as required during the washout period.
- 16 = Spontaneous AE reporting will be continuous throughout the study; however, AE assessments will be performed at each visit using non-leading questions.
- 17 = Retrieve/review compliance at these visits; investigational product and packet will not be re-dispensed.
- 18 = ECG and physical exam do not need to be repeated at Visit 6 if previously performed for Premature Discontinuation Visit. A brief physical exam may be performed at Visit 6 to document any changes from the previous exam.
- 19 = During all visits (including those conducted by telephone), site will review e-diary entries for compliance. Site will also retrain the subject on use of e-diary if needed.
- 20 Subjects without DLco testing in the previous 6 months may be enrolled with medical monitor approval.

Table 2:Schedule of Events – Treatment Period 2

	Treatment Period 2 ¹							Premature
	BaselineTreatmentFollow-up2I						Discontinuation	
Visit:	6		7	8	9		10	
	On-Site Visit		Phone Visit	Phone Visit	On-site Visit		On-Site Visit	
Treatment Day:	-1	13	8 (+/-1day)	15 (+/-1 day)	21	224	36 (+/-2days)	
Electrocardiogram (triplicate) ⁵							X^{17}	Х
Vital signs ⁶							Х	Х
Spirometry ⁷					Х			
Physical examination							X^{17}	Х
Urine pregnancy test							Х	Х
Serum pregnancy test	Х							Х
Clinical laboratory tests ⁹	Х				Х			Х
PK blood sampling					Х			
Cough monitor – Dispense/train on use	$X^{10,11}$				X ¹¹			
Cough monitor – Removal/return for downloading of		v 12				v 12		
data		Λ				Λ		
Cough frequency (via cough monitor)	Х	X ¹²			Х	X ¹²		
Cough Severity Numerical Rating Scale	Х		Х	Х	Х			Х
Fatigue Scale (Short Form 7a)	Х				Х			Х
Clinical Global Impression of Change					Х			
e-diary – Re-train on use	Х							
e-diary – Review compliance ¹⁸	Х		Х	Х	Х			
EXACT version 1.1 e-diary tool ¹³		<	Recorded	throughout	>			Х
Subjective Opiate Withdrawal Scale e-diary					X ¹⁴			X ¹⁴

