Contraceptive counseling (if applicable)	X		Х	Х	Х			
Dispense Subject Medication Symptom Log	Х							
Subject Medication and Symptom Log –			x	x	x			
retrieve/review/re-dispense			 	Λ	Λ			
Record/assess AEs, conmeds, and therapies (including restricted/prohibited medications) ¹⁵	Х		Х	Х	Х		Х	Х
Dispense Investigational Product blister card/dosing instructions	X ⁸							
Review Investigational Product compliance			Х	Х				
Retrieve Investigational Product blister card/ review					X		X ¹⁶	X ¹⁶
Final retrieval of e-diary, medication and symptom log							X	X

PK = pharmacokinetic; AE = adverse event; conmeds = concomitant medications

- 1 = Investigational product administration in each treatment period will be separated by a washout interval of 2 weeks between dosing.
- 2 = Follow-up will occur 14 \pm 2 days after the last administration of investigational product.
- 3 = First dose of investigational product for Treatment Period 2 is taken the evening of Day 1 after removal of the cough monitor.
- 4 = Last dose of investigational product for Treatment Period 2 is the morning dose of Day 22.
- 5 = Electrocardiogram (ECG) to be recorded prior to blood sampling when possible at scheduled visits where PK and/or clinical labs are obtained. Subjects should be in the supine position for at least 5 minutes prior to obtaining ECGs with all 3 tracings captured within a 3-5 minute window.
- 6 = Includes heart rate, blood pressure, respiratory rate, body temperature, and pulse oximetry. Vital signs should be taken prior to blood sampling and measured after the subject has been seated for at least 5 minutes.
- 7 = Performance of spirometry should adhere to ATS/ERS guidelines.
- 8 = A negative urine pregnancy test will be confirmed prior to randomizing any female subjects of childbearing potential.
- 9 = Blood and urine samples for clinical laboratory testing should be obtained after 8 hours of fasting whenever possible. Clinical chemistry, hematology, urinalysis, and coagulation will be assessed.
- 10 = Baseline values for the purposes of the statistical analysis of treatment effect on daytime cough frequency during that crossover period. First dose of investigational product on Treatment Day 1 will be taken after removal of the cough monitor.
- 11 = Monitor will be placed on the subject by site staff at the end of the visit.

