Subjects will return for Follow-up Visit 10 (Day 36) 14 days (+/- 2 days) after the last day of dosing in Treatment Period 2. Subjects will undergo the following assessments:

- Brief physical examination
- ECG (triplicate)
- Measurement of vital signs (blood pressure, heart rate, and respiratory rate), body temperature, and pulse oximetry

- Urine pregnancy test (females of childbearing potential)
- Collect investigational product blister card and assess investigational product accountability/compliance.
- Retrieve e-diary
- Retrieve and review Subject Medication and Symptom Log
- Record and assess adverse events, concomitant medications, and therapies (including restricted and prohibited medications)

6.3.3 **Premature Discontinuation Visit**

Subjects who complete investigational product treatment through the full study treatment course are considered to have completed treatment (even if some doses have been missed). Subjects who discontinue investigational product prior to Treatment Period 2 (Visit 10) will be considered to have prematurely discontinued and will be asked to complete the following visits (unless consent is withdrawn):

- If the decision to discontinue treatment is made during an onsite study visit (scheduled or unscheduled), perform the procedures and assessments outlined in the Premature Discontinuation Visit, regardless of where they are in the study visit schedule.
- If the decision to discontinue treatment is made while the subject is not at a study visit, schedule a visit as soon as possible, but no later than 2 weeks later, to perform the procedures and assessments described in the Premature Discontinuation Visit. Upon notification that the subject has permanently stopped dosing, the site should instruct the subject to begin entering their SOWS data daily via the e-diary.
- The subject should be scheduled to return to the clinic 2 weeks after completion of the Premature Discontinuation Visit for procedures and assessments outlined in the Follow-up Visit (Visit 6 if in Treatment Period 1 and Visit 10 if in Treatment Period 2).

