6.6 Risk/Benefit and Ethical Assessment

Nalbuphine has a long history of use in a parenteral formulation, generally for short-term, episodic use related to surgical interventions. The highest dose proposed in the current clinical study is 162 mg BID (324 mg daily dose), well below the highest recommended daily treatment of 144 mg IV dose (equivalent to 864 mg oral dose) for the currently available parenteral administered product. The high peak plasma concentrations that occur in the setting of parenteral use significantly exceed the peak levels observed with NAL ER oral dosing, an observation that is reassuring with respect to the potential for severe, acute toxicity.

Opiate drug class-related concerns such as the potential for physical dependence, linked to longterm use of opiates, is acknowledged. A requirement for completion of a 2-week safety observation period with daily SOWS reporting has been incorporated into the TR12 study. This will facilitate rapid identification and intervention for the respective relevant risks to subjects.

In addition, labeling of opiate-class drugs includes a warning that concomitant use of an opiate together with a benzodiazepine-class drug can increase the risk for respiratory depression, including a risk for respiratory arrest. This warning is based on post-marketing real world data, assessing the experience with a wide range of drugs in these 2 classes and in varied settings including recreational as well as therapeutic usage. In TR12, concomitant benzodiazepine use is not prohibited, and all subjects are informed of this risk through the study Informed Consent Form. At the time of that consent discussion, subjects who are identified as taking a concomitant benzodiazepine should receive the Patient Information Sheet on this topic, as should any subject for whom a concomitant benzodiazepine is subsequently prescribed.

With respect to the published literature addressing respiratory depression with nalbuphine, one relevant study has been identified; which evaluated the respiratory effects of serial intravenous administration of nalbuphine in healthy volunteers. The results were interpreted by the authors as demonstrating a "ceiling" effect for respiratory depression (*Gal et al 1982*). In previous clinical trials with NAL ER, a total of 41 subjects have received concomitant benzodiazepines while receiving NAL ER, and none of these individuals experienced any event of respiratory depression.

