8.4.10 Subjective Opiate Withdrawal Scale

Subjects will complete the SOWS on a daily basis for 14 days following the last dose of investigational product in each treatment period. Any subject discontinued from investigational product, prior to completion of the study, will also complete the SOWS daily for the 14 days following the last dose of investigational product (unless consent is withdrawn). The SOWS is a self-administered scale for grading opioid withdrawal symptoms.

The SOWS is provided in *Appendix 4*. Subjects will complete the SOWS via the study specific e-diary.

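### The protocol both collects the e-diary at the Premature Discontinuation Visit and requires 14 days of withdrawal-scale entries on it after the last dose; the passages need to be reconciled

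*Protocol*

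**What the plan says.** **Text that collects the device at discontinuation.** Protocol section 8.2.2: "The subject will return the e-diary to the site at the follow-up visit of Treatment Period 2 or discontinuation visit". In section 6.2, the Table 1 row "Retrieval of e-diary, medication and symptom log" and the Table 2 row "Final retrieval of e-diary, medication and symptom log" are each marked in both the Follow-up column and the Premature Discontinuation column. SAP Appendices 1 and 2 carry the same rows and marks.

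**Text that needs the subject to keep it.** The SOWS footnote to the schedule reads: "Subjective Opiate Withdrawal Scale will be completed daily via e-diary for 14 days following discontinuation of investigational product regardless of when this occurs". Section 8.4.10 says that a subject taken off investigational product early "will also complete the SOWS daily for the 14 days following the last dose of investigational product (unless consent is withdrawn", and adds: "Subjects will complete the SOWS via the study specific e-diary". Under section 6.3.3, a subject who stops between visits is told to start daily SOWS entries on the e-diary once the site knows that dosing has ended.

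**Text that implies later collection.** Section 6.3.3 brings early stoppers back two weeks after the Premature Discontinuation Visit, for Visit 6 or Visit 10 depending on the period. The procedure lists for both visits include e-diary retrieval. The SOWS footnotes also have the site check entries through the e-diary portal during washout.

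**Timing of the discontinuation visit.** If the decision is made at an on-site visit, the site is to "perform the procedures and assessments outlined in the Premature Discontinuation Visit, regardless of where they are in the study visit schedule". Otherwise the visit is to be held as soon as possible and within two weeks (section 6.3.3).

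**The concern.** In both schedules the Premature Discontinuation column marks the SOWS e-diary, which begins a 14-day task, and also marks removal of the device on which the task is done. The protocol gives no paper form or other device for the SOWS. Where paper is intended, it says so, as for the cough severity scale at screening (section 8.2.4).

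Safety and tolerability is a primary objective, and section 6.6 relies on this instrument: "A requirement for completion of a 2-week safety observation period with daily SOWS reporting has been incorporated into the TR12 study". Subjects who stop early are of direct interest for that question. Any loss would fall on them selectively, because completers take the last dose on Day 22 and hand the device back at Day 36. A site that holds the discontinuation visit promptly, as section 6.3.3 asks, would lose the most entries. Portal checks would have nothing to show once the device is back at the site.

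**Working it through.** No power, sample-size or error-rate figure is involved. The check sets the passages side by side and counts days.

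**Inputs**
- Required SOWS window: days 1 to 14 after the last dose (section 8.4.10; Table 1 and Table 2 SOWS footnotes).
- Day of the Premature Discontinuation Visit, counted from the last dose: *k*. It is 0 if the last dose is on the day of an on-site decision. For an off-site decision the visit falls 0 to 14 days after the decision (section 6.3.3).
- Planned numbers: about 60 randomised, 44 with complete data, dropout up to 26% (section 11.1).

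**Entries lost if the device is handed in at that visit**
- Return-day entry made: lost = 14 − min(*k*, 14).
- Return-day entry not made: lost = 14 − min(max(*k* − 1, 0), 14).

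| Visit day *k* | Lost, return-day entry made | Lost, return-day entry not made |
|---|---|---|
| 0 | 14 | 14 |
| 1 | 13 | 14 |
| 3 | 11 | 12 |
| 7 | 7 | 8 |
| 13 | 1 | 2 |
| 14 | 0 | 1 |
| 15 or later | 0 | 0 |

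These are losses from device return alone. An off-site stopper begins entries only once the site has been notified, so any delay there is additional.

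**Entries lost if the device is kept to the follow-up visit.** That visit is two weeks after the discontinuation visit, so return is on day *k* + 14, which is day 14 or later. The loss is 0 if the return-day entry is made, and at most 1, when *k* = 0, if it is not. If a two-day early window were used for this visit, the earliest return would be day 12. The same formulas then give 14 − 12 = 2 or 14 − 11 = 3 entries lost.

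**How many subjects.** The plan's own figure reproduces: 44 / (1 − 0.26) = 59.5, rounded up to 60. Planned non-completers are 60 − 44 = 16 (60 × 0.26 = 15.6). This is a ceiling for scale, not an estimate of those affected.

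**The case against.** The strongest reply is that a sensible site would not collect the device early. The same column calls for SOWS by e-diary, the footnote expects portal checks in washout, section 6.3.3 itself orders no retrieval at the discontinuation visit, and the Visit 6 and Visit 10 lists both include it. A site following those passages loses nothing. This stands, and it makes the loss conditional. It does not remove the conflict, because section 8.2.2 and both tables say the opposite and no passage is given precedence.

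It is also fair to say that the 14-of-14 case may be uncommon. Days 8 and 15 are telephone visits and the only scheduled on-site visit during dosing is Day 21. A stop during titration would therefore usually be decided off site, unless at an unscheduled visit, and the subject may already have made some entries.

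A reader might infer three stronger things that the documents do not support:
- *That all 16 or so planned non-completers lose SOWS data.* The 26% is an allowance for reaching 44 complete subjects. It can include subjects who withdraw consent (exempt from SOWS), subjects who finish Period 1 and its washout but never start Period 2, and subjects whose visit falls near day 14.
- *That this conflict is why the SOWS summary would mainly describe completers.* With 44 of 60 planned to complete, it would do so even with perfect capture.
- *That withdrawal would go unobserved.* Adverse event collection, the special-interest category that covers withdrawal complaints (section 10.2.3), the instruction to contact the investigator about significant symptoms (section 6.5) and the follow-up visit all remain. They are weaker than a daily scale: questioning is general (section 8.4.1), and special-interest events are probed only when reported spontaneously.

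**Conclusion.** The inconsistency is real, is in the current text, and appears in the protocol body, both protocol schedules and both SAP copies. As written, a site that applies section 8.2.2 and the retrieval rows removes the only SOWS instrument before the required window has closed, unless the visit falls about 14 days or more after the last dose. The loss then runs from all 14 entries to none, depending on the visit day.

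This rests on two assumptions: that the retrieval rows are followed literally, and that no undocumented route for SOWS entry exists. The number of subjects affected cannot be derived from the documents. Sixteen is a loose upper bound on the planned numbers, and SAP section 4.14 records that the study ended before reaching its planned size.

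The consequence is limited to withdrawal data that SAP section 4.12.10 lists and summarises descriptively by treatment and study day. The primary efficacy analysis and the sample size are unaffected. Because the data serve a primary safety objective and the correction is cheap, it should be made.

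**What to change.** 1. In Tables 1 and 2 and in SAP Appendices 1 and 2, split the combined retrieval row. Keep the medication and symptom log marks as they are, including at the Premature Discontinuation Visit. Mark the e-diary for retrieval at the follow-up visit only. Deleting the existing mark without splitting the row would also drop retrieval of the log.
2. Reword section 8.2.2 so that the e-diary is returned at the Period 2 follow-up visit or, when treatment is stopped early, at the follow-up visit two weeks after the Premature Discontinuation Visit (Visit 6 in Period 1, Visit 10 in Period 2). Simply striking the reference to the discontinuation visit would leave a Period 1 early stopper with no return point.
3. State that the device is not handed in before the day-14 SOWS entry, so that an early visit does not shorten the window.
4. For subjects already handled, report how many of the 14 SOWS days each early stopper provided, by treatment received. SAP section 4.15 records that recruitment has ended, so this may be the main step still open for this trial.

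Cost: one row split in each of four schedule tables, a reworded sentence in section 8.2.2 and one added statement, with no new visit, procedure or device. The subject keeps the e-diary about two weeks longer, with a small risk that it is not returned. Step 4 adds one short table or listing.
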